**ANCILLARY REVIEWS**

Which ancillary reviews do I need and when do I need them? Refer to HRP-309 for more information about these ancillary reviews.			
Select yes or no	Does your study...	If yes...	Impact on IRB Review
 Yes  No	Include Gillette resources, staff or locations	Gillette Scientific review and Gillette Research Administration approval is required. Contact: [contact]	Required prior to IRB submission
 Yes  No	Involve Epic, or Fairview patients, staff, locations, or resources?	The Fairview ancillary review will be assigned to your study by IRB staff Contact: [contact]	
 Yes  No	Include evaluation of drugs, devices, biologics, tobacco, or dietary supplements or data subject to FDA inspection?	The regulatory ancillary review will be assigned to your study by IRB staff Contact: [contact]  See: https://policy.umn.edu/research/indide	
 Yes  No	Require Scientific Review? Not sure? See guidance on next page.	Documentation of scientific merit must be provided. Contact: [contact]	
 Yes  No	Relate to cancer patients, cancer treatments, cancer screening/prevention, or tobacco?	Complete the CPRC application process. Contact: [contact]	
 Yes  No	Include the use of radiation? (x-ray imaging, radiopharmaceuticals, external beam or brachytherapy)	Complete the AURPC Human Use Application and follow instructions on the form for submission to the AURPC committee. Contact: [contact]	
 Yes  No	Use the Center for Magnetic Resonance Research (CMRR) as a study location?	Complete the CMRR pre-IRB ancillary review Contact: [contact]	
 Yes  No	Include the use of recombinant or synthetic nucleic acids, toxins, or infectious agents?	Complete the IBC application via eprotocol.umn.edu Contact:	

MEDICAL PROTOCOL (HRP-590)  
 PROTOCOL TITLE: **Cilostazol for HFpEF**  
 VERSION DATE: 05.16.2020

 Yes  No	Include the use of human fetal tissue, human embryos, or embryonic stem cells?	Contact OBAO for submission instructions and guidance	application process.
 Yes  No	Include PHI or are you requesting a HIPAA waiver?	If yes, HIPCO will conduct a review of this protocol. Contact: [contact]	
 Yes  No	Use data from the Information Exchange (IE)?	The Information Exchange ancillary review will be assigned to your study by IRB staff Contact: [contact]	Approval must be received prior to IRB approval.  These groups do not have a separate application process but additional information from the study team may be required.
 Yes  No	Use the Biorepository and Laboratory Services to collect tissue for research?	The BLS ancillary review will be assigned to your study by IRB staff. Contact: [contact]	
 Yes  No	Have a PI or study team member with a conflict of interest?	The Col ancillary review will be assigned to your study by IRB staff Contact: [contact]	
 Yes  No	Need to be registered on clinicaltrials.gov?	If you select "No" in ETHOS, the clinicaltrials.gov ancillary review will be assigned to your study by IRB staff Contact: [contact]	
 Yes  No	Require registration in OnCore?	If you select "No" or "I Don't Know" in ETHOS, the OnCore ancillary review will be assigned to your study by IRB staff Contact: [contact]	

MEDICAL PROTOCOL (HRP-590)  
 PROTOCOL TITLE: **Cilostazol for HFpEF**  
 VERSION DATE: 05.16.2020

**REVISION HISTORY**

Revision #	Version Date	Summary of Changes	Consent Change?

NOTE: Leave this section blank for the initial submission. The revision history should be documented for modifications to approved studies.

**ABBREVIATIONS/DEFINITIONS**

Include any abbreviations or definitions for key or technical terms you use in your protocol.

- HFpEF                      Heart Failure with a preserved ejection fraction
- NTproBNP                N-terminal B-type natriuretic protein (heart failure blood marker)

## **1.0 Objectives**

### *1.1 Purpose:*

Determine if cilostazol improves symptoms and NTproBNP levels (heart failure blood marker) in heart failure with preserved ejection fraction (HFpEF) – a prevalent syndrome without evidence-based treatment.

This will be assessed in a prospective 1-month single blinded study with 2 cross-overs (n-of-1 study design with placebo and cilostazol)

### *1.2 Primary outcome:*

1. standardized heart failure questionnaire  
(sample provided at the end of the consent document)

### *1.3 Secondary outcome:*

2. NTproBNP

## **2.0 Background**

### *2.1 Significance of Research Question/Purpose:*

Heart failure (HF) is the #1 reason for hospital admissions. About half of the patients with HF have a preserved ejection fraction (HFpEF). There is no evidence-based treatment for HFpEF. We recently reported that beta-blockers increase the risk for HF admissions in HFpEF, in part by their heart rate lowering effects (1-3). On the contrary, we found that elevating the heart rate with pacemakers conveys significant clinical benefits e.g. reduction in heart failure symptoms, lowering filling pressures and an increase in walk distance (4-6). Cilostazol increases the heart rate by about 5-8 beats per minute and has other potentially beneficial HFpEF effects such as peripheral vasodilation, lusitropic effects (acceleration of relaxation) and dromotropic effects (improved cardiac electrical conduction). By activating protein kinase A, cilostazol may also phosphorylate titin, which would reduce myocardial stiffness (6).

### *2.2 Preliminary Data:*

Cilostazol is approved for the use in peripheral artery disease and has been used in patients with diastolic dysfunction-induced atrial fibrillation and HFpEF. This results in a symptomatic relief and significant reductions in the heart failure blood marker BNP (7,8). In our own clinical experience, cilostazol reduces HFpEF symptoms and lowers NTproBNP by about 25% to suggest a clinical benefit that is in line with the cilostazol-induced changes in BNP in patients with atrial fibrillation (7,8). No adverse effects were noted in our own HFpEF patients that chronically take cilostazol.

## 3.0 Study Endpoints/Events/Outcomes

Endpoint/Event/Outcomes:

1. standardized heart failure questionnaire
2. NTproBNP

## 4.0 Study Intervention(s)

### 4.1 Description:

We propose a n-of-1 study design using the standard dose cilostazol formulation of 100mg twice a day approved in peripheral vascular disease. The patients will be blinded and serve as their own controls with two crossovers (cilostazol – placebo – cilostazol - placebo). This exploratory study is neither designed nor powered to seek a change in

[figure not shown]

the drug approval and thereby does not require an FDA investigational new drug (IND) application (see section 4.1). The study aims to minimize in-person visits during the ongoing COVID-19 pandemic.

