## **15.0 Statistical Considerations**

*15.1* Data Analysis Plan:

Primary outcomes

**KCCQ heart failure questionnaire:** paired parametric test (t-test) of placebo average composite score and the cilostazol average composite score.

**NTproBNP:** Relative changes in NTproBNP level (placebo versus cilostazol) will be compared by paired parametric testing (t-test).

*15.2* Power Analysis:

In a recent large HFpEF clinical trial of sacubitril/valsartan the baseline KCCQ score was  $71 \pm 19$ . A sample size of 18 would provide us with 80% power to detect a 25% relative difference using a 2-sided test. We propose a sample size of 25 participants to ascertain 18 or greater completed studies. In a recently completed pacemaker study that leads to a similar increase in heart rate we found a beneficial outcome in a heart failure questionnaire in n=22 participants (see reference #4, Wahlberg et al.).

*15.3* Statistical Analysis:

Linear mixed-effect models determine the effect of cilostazol on the primary outcome, accounting for inter-patient differences and treatment assignment and sequences. For the primary endpoint, the KCCQ total score at the end of each week (week 1 to 4) is the dependent variable, while the treatment (cilostazol versus placebo) is the independent variable. Patient identifier and treatment sequence (binary variable marking the start of the treatment with placebo or cilostazol) are entered as random effects. The same approach was taken to assess the effect of cilostazol on NT-proBNP levels, after log-transforming NT-proBNP values given their skewed distribution. To determine the

treatment effect paired analyses of subsequent treatment periods will be performed (Wilcoxon test) to match weeks and the days within the treatment period.

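### Section 4.1 gives one treatment order while 15.3 models two starting treatments; if the single order applies, the NTproBNP comparison cannot be separated from time

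*Combined protocol and SAP*

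**What the plan says.** Section 4.1 describes an n-of-1 design in which patients "serve as their own controls with two crossovers (cilostazol – placebo – cilostazol - placebo"). Sections 1.1 and 5.1 repeat the two crossovers and the single blind, but do not mention randomisation. Section 4.3 has the investigational pharmacy preload the monthly pill box without saying in which order.

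Section 15.3 describes something different. Its mixed model is said to work by "accounting for inter-patient differences and treatment assignment and sequences", and patient identifier and "treatment sequence (binary variable marking the start of the treatment with placebo or cilostazol) are entered as random effects". The only fixed term named is treatment; there is no week or period term. For the biomarker, "The same approach was taken to assess the effect of cilostazol on NT-proBNP levels", on the log scale. Section 15.3 adds that "paired analyses of subsequent treatment periods will be performed (Wilcoxon test) to match weeks and the days within the treatment period".

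Section 15.1 plans a "paired parametric test (t-test) of placebo average composite score and the cilostazol average composite score" for KCCQ. For the biomarker it says: "Relative changes in NTproBNP level (placebo versus cilostazol) will be compared by paired parametric testing (t-test"). NTproBNP is a secondary outcome in 1.3 but is listed among the primary outcomes in 15.1.

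Sections 4.1 and 5.2 place the KCCQ calls on days 7, 14, 21 and 28, and the two NTproBNP draws on days 5-7 and 25-28.

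**The concern.** The two sections cannot both be taken literally. If every patient starts on cilostazol, the sequence variable in 15.3 has one value and nothing can be estimated from it. If some start on placebo, 4.1 is incomplete, and no readable text says who starts on what or how that is decided.

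The answer matters most for NTproBNP, which has only two samples per patient. Under the 4.1 order, every cilostazol value comes from the first week and every placebo value from the fourth. Any drift over the month, from regression to the mean, diuretic changes or recovery after an admission, would be read as a drug effect or would hide one. KCCQ is less exposed because the treatments alternate weekly, but cilostazol is always one week ahead of placebo. Improvement over the month then counts against cilostazol, and worsening counts in its favour. Because the boxes are loaded in advance, the order cannot be repaired at analysis.

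**Working it through.** **Inputs.** From the documents: KCCQ 71 with SD 19, n = 18 completers, 25% relative difference = 0.25 × 71 = 17.75 points, two-sided (15.2); NTproBNP about 25% lower on cilostazol (2.2); the call and draw days above. Inferred: four one-week periods, from the weekly calls and the week 1 to 4 wording in 15.3. Assumed: alpha 0.05, all trends, and all paired SDs. The 19 is a baseline SD, not the SD of a within-patient difference.

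**The plan's own figure.** Section 15.2 states: "A sample size of 18 would provide us with 80% power to detect a 25% relative difference using a 2-sided test". It reproduces: 2 × [19 × (1.960 + 0.842) / 17.75]² = 17.99, or 18. This is the per-arm number for two independent groups, and treatment order does not enter it. A paired t-test with a paired SD of 19 has 96% power at n = 18, so the power figures below start from 96%, not 80%.

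**NTproBNP, single order: identifiability.** Code treatment as (1, 0) and the late draw as (0, 1) over the two samples. They sum to the intercept column (1, 1), so intercept, treatment and period have rank 2 of 3. Drug and time are completely aliased, whatever the size of any trend.

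**NTproBNP, single order: size.** The gap is 25 − 7 = 18 to 28 − 5 = 23 days; between midpoints it is 26.5 − 6 = 20.5 days = 2.93 weeks. With weekly change g, observed ratio = true ratio / (1 + g)^2.93.

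| Weekly change | True ratio 0.75 | True ratio 1.00 |
|---|---|---|
| fall 1% | 0.772 (looks like 23% lower) | 1.030 (3% higher) |
| fall 3% | 0.820 (18% lower) | 1.093 (9% higher) |
| fall 5% | 0.872 (13% lower) | 1.162 (16% higher) |
| rise 1% | – | 0.971 (3% lower) |
| rise 3% | – | 0.917 (8% lower) |
| rise 5% | – | 0.867 (13% lower) |

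Across the 18 to 23 day window, the row for a 3% fall runs 0.811-0.829 and 1.081-1.105.

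**KCCQ, single order: bias.** Cilostazol weeks average (1 + 3)/2 = 2 and placebo weeks (2 + 4)/2 = 3, so cilostazol minus placebo shifts by −1 × the weekly slope. The t-test in 15.1 and the mixed model in 15.3 both carry this shift. The Wilcoxon depends on which weeks are paired: 1 v 2 and 3 v 4 give −1; adding 2 v 3 gives (−1 + 1 − 1)/3 = −1/3.

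**KCCQ, single order: test behaviour.** Noncentrality = shift / (SD/√18), df 17, critical t 2.110. With no drug effect and an improvement of 2 points per week:

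| Paired SD | Noncentrality | Rejects against cilostazol | Rejects in favour | Total |
|---|---|---|---|---|
| 5 | −1.70 | 36.0% | 0.02% | 36% |
| 10 | −0.85 | 12.3% | 0.3% | 13% |
| 19 | −0.45 | 6.2% | 0.9% | 7% |

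Worsening of 2 points per week is the mirror image, with false benefit of 36%, 12% and 6%. For a true 17.75-point effect at SD 19, improvement of 1, 2 or 3 points per week lowers power from 96% to 94%, 91% or 87%.

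**Two orders.** Without a period term, the remaining bias is (n1 − n2)/n of the single-order bias: 0 at 9:9, and (12 − 6)/18 = 1/3 at 12:6. With the trends above, the 12:6 residue is 2 × 1/3 = 0.67 KCCQ points and 0.97^(−2.93/3) = 1.030, or 3%, on NTproBNP. Unrestricted 1:1 randomisation of 18 gives 12:6 or worse with probability 0.238.

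**Cost of a week term for KCCQ, patient effects in the model.** Categorical week with two orders multiplies the treatment variance by 1.00 at 9:9 and 1.125 at 12:6. Under one order a linear week term multiplies it by 1.25. Categorical week is then not estimable alongside treatment (rank 4 of 5 for intercept, treatment and three week terms).

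**The case against.** The flow diagram in 4.1 is not in the readable text, and 5.2 refers to it on this very point. It may show two orders, and an allocation method may lie there too. The wording in 15.3 would be pointless if everyone followed one order, so the parenthesis in 4.1 may only illustrate the alternation. With two balanced orders, linear-trend bias is zero, leaving a wording conflict and a missing period term. Every trend is assumed, the 36% needs a paired SD of 5 that no document supports, and 4.1 calls the study exploratory.

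Much of this stands, and it is why the bias figures are conditional on the single order. The KCCQ effect is modest at SD 19. But the conflict between 4.1 and 15.3 is in the text under either reading. The NTproBNP aliasing under one order needs no trend assumption, and an exploratory comparison still has to be estimable. A sequence term does not stand in for a period term: it is constant within a patient and cannot remove a trend from within-patient differences.

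**Conclusion.** The concern holds. Sections 4.1 and 15.3 contradict each other on treatment order, and no readable text states an allocation method. If the 4.1 order applies to everyone, the NTproBNP comparison cannot be interpreted as a drug effect; assumed drifts of 1% to 5% per week move the apparent effect by roughly 2 to 16 percentage points, in either direction. KCCQ remains estimable if any trend is linear and is modelled, but the planned analyses do not model one, and they carry a shift of one week's trend (one third of a week under one reading of the Wilcoxon). If two orders apply and completers split equally, linear-trend bias vanishes; an unequal split leaves part of it. The sizes rest on inferred one-week periods, assumed trends and assumed paired SDs. The contradiction and the aliasing under one order do not depend on the assumed trends or SDs.

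**What to change.** Reconcile 4.1 with 15.3 and state the order or orders in the text, not only in a diagram.

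**If two orders are intended:**
- State in 4.1 and 5.1 that the starting treatment is randomised 1:1 (C-P-C-P or P-C-P-C) in balanced blocks, from a list held by the pharmacy that already preloads the boxes.
- Add week as a categorical fixed effect to the KCCQ model in 15.3.
- Analyse log NTproBNP as a two-period crossover with a period term.

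**If the single order is kept:**
- Delete the sequence term.
- Add a linear week term for KCCQ, noting that it removes only a linear trend.
- Report NTproBNP descriptively, as not separable from time.

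Either way, say in 15.3 which weeks the Wilcoxon pairs.

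The cost is protocol wording and, for two orders, an allocation list; no extra patients, visits or samples. Two orders use three degrees of freedom for week in KCCQ and one for period in NTproBNP, with no KCCQ variance inflation at 9:9 and 1.125-fold at 12:6. The single-order fallback inflates the KCCQ treatment variance 1.25-fold and gives up inference on NTproBNP.

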#### Study Flow:

1. Screening of clinic patients
2. Informed Consent
3. Study drugs distribution by the pharmacy
4. Study start (1st of month)
5. Interventions (see below)
6. Study end (end of month)

#### **Cilostazol 100mg BID (white) versus Placebo BID (colored or different shape – to confirm adherence)**

The cilostazol and placebo pills are in a preloaded pill-organizer box (see below).

- study start at first day of the month (to facilitate adherence)
- two in person study visits on **day 5-7** and **day 25-28** for blood draw **and vital signs**
- four scheduled phone calls (days: **7, 14, 21 and 28**) : heart failure questionnaires

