4.4 Biosafety: N/A

4.5 Stem Cells: N/A

4.6 Fetal Tissue: N/A

## 5.0 Procedures Involved

5.1 Study Design: prospective single blind placebo controlled n=1 study with 2 cross-overs

5.2 Study Procedures:

- NTproBNP on cilostazol and on placebo (see flow diagram) day 5 to 7 (5mL's) and day 25 to 28 (5 mL's) at any Fairview Lab site.
- Kansas City Heart Failure Questionnaire (KCCQ-12) will be administered by PI phone call day 7, 14, 21 and 28
- Baseline patient characteristics collected from Fairview EPIC

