## **13.0 Risks to Participants**

*13.1* Foreseeable Risks:

Headaches 34% (+20% over placebo)

Palpitations 10% (+9% over placebo)

Diarrhea 19% (+12% over placebo)

Additional Risks:

left ventricular outflow tract obstruction, any type of heart failure, bleeding

dyscrasias, blood dyscrasias and drug interactions.

*13.2* Reproduction Risks:

minimal, HFpEF is a disease outside the typical reproductive ages

*13.3* Risks to Others:

N/A

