## **14.0 Potential Benefits to Participants**

*14.1* Potential Benefits:

moderate chance (>30%) at improving heart failure symptoms within 48h after first dose of cilostazol

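### Placebo is deliberately made to look different from cilostazol in a within-patient crossover, so the patient blind cannot be relied on for the patient-reported KCCQ-12

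*Combined protocol and SAP*

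**What the plan says.** Three places state the blinding. Section 1.1 describes a "prospective 1-month single blinded study with 2 cross-overs", section 5.1 a "prospective single blind placebo controlled n=1 study with 2 cross-overs", and section 4.1 says "The patients will be blinded and serve as their own controls with two crossovers (cilostazol – placebo – cilostazol - placebo".

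The product description, also in section 4.1, makes cilostazol white and specifies "Placebo BID (colored or different shape – to confirm adherence". The difference is therefore intended and has a stated reason.

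Section 4.3 has the investigational pharmacy load both products into one monthly box with 31 removable daily vials, which is handed or shipped to the patient. No section mentions a matched placebo, over-encapsulation, a double dummy or a check of the blind.

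The primary outcome in section 1.2 is a "standardized heart failure questionnaire". Section 5.2 identifies it as the KCCQ-12, taken by the principal investigator by phone on days 7, 14, 21 and 28. Nothing masks the caller or the analyst.

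**The concern.** In a parallel-group trial each patient sees one product, and a difference in look may go unnoticed. Here every patient handles both, so the look marks each switch and shows which periods go together. What stays hidden is which look is the active drug.

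Once a patient forms a view on that, it applies to all later periods with the same pill. Expectation then enters the cilostazol-placebo difference in the same direction in both cycles. Neither averaging over periods for the paired t-test (section 15.1) nor the mixed model (section 15.3) can separate it from a drug effect.

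The KCCQ-12 rests on the patient's own judgement, and the patient blind is the only masking the plan claims. The results feed a publication (section 12.3) and an individual benefit or no-benefit message that may lead to a talk with the treating provider about a prescription (section 7.1).

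**Working it through.** **1. The statements side by side.**

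- Blinding claimed: the patient only (1.1, 4.1, 5.1).
- Appearance: white versus another colour or shape (4.1).
- Exposure: both products, alternating, from one box (4.1, 4.3). The weekly length of the periods is read from the call days and from section 15.3, which uses the score at the end of each of weeks 1 to 4.
- Certain consequence: the patient can see the switches and the grouping of weeks.
- Not certain: that the patient knows which product is active.

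**2. Cues available to identify the drug.** Section 13.1 gives rates on cilostazol and the excess over placebo, so the placebo rates follow by subtraction.

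| Symptom | Cilostazol | Excess | Placebo |
|---|---|---|---|
| Headache | 34% | 20 | 34 - 20 = 14% |
| Diarrhea | 19% | 12 | 19 - 12 = 7% |
| Palpitations | 10% | 9 | 10 - 9 = 1% |

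Section 14.1 adds a "moderate chance (>30%) at improving heart failure symptoms within 48h after first dose of cilostazol". No time window is given for the side-effect rates, so they cannot be read as rates per week.

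**3. The plan's own sample size.** A difference of 0.25 x 71 = 17.75 points and an SD of 19 (section 15.2), with an assumed two-sided alpha of 0.05 and 80% power, give 2 x (1.960 + 0.842)^2 x 19^2 / 17.75^2 = 17.99, so 18. This is the per-arm formula for independent groups. It reproduces the stated 18 and does not depend on pill appearance, so matching the placebo leaves the sample size unchanged.

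**4. What a net expectation bias would do.** Take no true drug effect and let b be the bias in the mean difference, averaged over all patients. The paired t statistic then has a noncentral t distribution with n - 1 = 17 degrees of freedom and noncentrality b x sqrt(18) / SD. The test rejects beyond plus or minus 2.11. The documents give neither b nor the SD of the per-patient difference; both are assumed. The SD range of 8 to 15 covers 19 x sqrt(1 - rho) for the difference between two-period averages: 13.4 at a correlation of 0.5 and 8.5 at 0.8.

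| Net bias b | SD 8 | SD 10 | SD 15 |
|---|---|---|---|
| 0 | 5% | 5% | 5% |
| 2 | 17% | 13% | 8% |
| 3 | 32% | 22% | 13% |
| 5 | 71% | 52% | 27% |

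More patients do not help. With all 25 completing and SD 10, a 5-point bias gives 67%.

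**5. If only some patients identify the drug.** Net bias is roughly (share guessing right minus share guessing wrong) x individual effect. As an illustration, let the informed share run from the headache excess of 20% to the sum of the three excesses, 20 + 12 + 9 = 41%, with all other guesses cancelling. An individual effect of 5 points then gives a net bias of 0.20 x 5 = 1.0 to 0.41 x 5 = 2.05 points. Rejection is about 7-13% at SD 10, and 6-18% over SD 8 to 15.

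**The case against.** A reader might infer that the blind is lost outright, or that many patients would work out the drug in their first cilostazol week. The documents support neither. They do not say that patients are told which look is active; the consent pages and the flow figure were not available to settle it. About two-thirds of patients would have no headache on cilostazol, and about 14% would have one on placebo, which would mislead some guesses. Side effects can also unmask patients when pills are identical. What the visible difference adds is that a guess carries over to the other weeks.

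A reader might also infer that a positive KCCQ-12 result could never be attributed to the drug. That goes too far: the size of the bias is unknown, and NT-proBNP, a laboratory value, is less exposed. Section 4.1 also calls the study exploratory.

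The adherence reason has some merit. Asking about pill colour by phone could check that the scheduled product is being taken on a given day, which a final count cannot date. But the look of a pill does not show that it was swallowed.

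These points limit the size of the concern. They do not reconcile a stated patient blind with products made to be told apart, and NT-proBNP does not protect the KCCQ-12 comparison.

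**Conclusion.** The point holds as a contradiction between the stated patient blind and the specified pill appearance. Concealment of the switches and of the grouping of weeks is gone for every patient who looks at the pills. Concealment of which product is active is weakened to an unknown degree, and the plan has no check on it. The patient blind therefore cannot be relied on for the primary outcome.

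The rejection rates of 8-17%, 13-32% and 27-71% are conditional on a net bias of 2, 3 or 5 points averaged over all patients, no true effect, 18 completers, an assumed alpha of 0.05 and an assumed SD of 8 to 15. They show sensitivity and do not forecast the trial's error rate. If a minority identify the drug, the lower figures in step 5 are the fairer guide. The contradiction itself rests on none of these assumptions, and it cannot be repaired once the data are collected.

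**What to change.** In section 4.1, replace the distinguishable placebo with one identical in look to the active pill. This can be a matching tablet, or both products over-encapsulated by the pharmacy that already supplies and loads the boxes. Check adherence by counting the pills left in the returned box. After the last KCCQ-12, ask which weeks the patient believes were cilostazol, and report the answers with the primary result.

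If matching is not done, stop describing the study as patient-blinded in sections 1.1, 4.1 and 5.1, and state that the KCCQ-12 result is open to expectation bias.

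The costs are pharmacy work for 25 patients (the documents give no price, but it should be small), one added question, loss of the visual adherence cue, and a step to return the box. That last step needs planning: the final visit falls on days 25-28, the box holds 31 daily vials, and the study aims to keep in-person visits few. The sample size does not change.
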